1.1 Background

Acute heart failure (AHF) is recognized as a major and escalating public health problem with high disease prevalence associated with poor prognosis. It is the leading medical cause of hospitalization among patients over 65 years of age in the United States, European countries, Australia and New Zealand, with a significant cost burden for the health care systems (McMurray 1998, Fonarow 2008, Roger and Go 2012).

Despite the undoubtedly clinical importance of AHF, no universally accepted definition exists, but the condition is generally considered to represent the relatively abrupt onset of symptoms and signs secondary to abnormal cardiac function. The cardiac dysfunction can be related to systolic or diastolic myocardial dysfunction, to acute valvular dysfunction, to pericardial tamponade, to abnormalities in cardiac rhythm, or to preload and afterload mismatch. It is a life-threatening condition that requires immediate medical attention, and usually leads to urgent admission to hospital (McMurray et al 2012). In most cases, AHF arises as a result of deterioration in patients with a previous diagnosis of heart failure (HF) (where the term *acute decompensation* is often applied), but it can also occur as the first manifestation of a failing heart (acute *de novo* heart failure) (McMurray et al 2012). AHF should be considered as a heterogeneous set of syndromes, characterized by reduced cardiac output, tissue hypoperfusion and increase in the pulmonary capillary wedge pressure and tissue congestion. Such set of syndromes induce metabolic abnormalities and organ damage, such as renal and liver damage (Metra et al 2010a; Metra et al 2012).

Epidemiological registries and surveys in Europe (Zürich-Helsinki, EFICA, Italian Acute Heart Failure Survey, Euro Heart Survey I and II, British NHS survey) (Rudiger et al. 2005, Zannad et al 2006, Tavazzi et al 2006, Cleland et al 2003, Nieminen et al 2006, Nicol et al 2008), in USA (ADHERE) (Adams et al 2005), in ASIA Pacific region (ATTEND) (Sato et al 2010), and across 9 countries in 4 continents (ALARM-HF) (Follath et al 2011) provided several clues for diagnosis and classification of AHF. These multicenter hospital-based registries and surveys have shown that the typical patient is elderly, with a history of heart failure, coronary artery disease and hypertension. Patient presentation may vary, encompassing worsening congestion, worsening chronic heart failure, pulmonary edema, hypertensive crisis, or cardiogenic shock. Patients typically spend several days in the intensive care unit, with longer admissions in Europe than the United States (Dar and Cowie 2008). The vast majority of patients symptomatically improve during hospitalization; however, their early post-discharge rehospitalization and mortality rates continue to be high (Gheorghiade et al 2009, Bueno et al, 2010).

The main clinical challenges in managing AHF patients are to achieve the optimal and sustained resolution of patient congestion aiming for prevention of in-hospital worsening of heart failure (WHF) and organ damage.

The therapeutic approach of AHF has remained the same for decades, being the use of the most acute treatments empirical. Conventional treatment for AHF consists of loop diuretics to reduce fluid overload, plus the addition of nitrates (oral, sublingual or IV) where required to ease vasoconstriction. None of the currently available treatments can demonstrate positive

outcome benefits from randomized clinical trials and, according to the latest ESC-ESH guidelines, treatment in AHF remains largely opinion-based with little good evidence to guide therapy (McMurray et al 2012).

In-hospital worsening of heart failure is considered a clinically relevant end-point in the evaluation of treatment success for AHF (Zannad et al 2013). WHF is defined as a persistence or worsening of symptoms during the acute phase of a heart failure episode requiring intensification of therapy in patients already hospitalized for their acute decompensation (similar to the RELAX-AHF WHF definition). Approximately 10–30% of patients may experience in-hospital WHF in the first few days following hospital admission for AHF (Cotter et al 2010; Weatherley et al 2009).

WHF is a distinct clinical event that represents a severe deterioration of AHF signs/symptoms requiring urgent intervention. Also, it is an event that profoundly alters the patient's disease trajectory. Published data clearly demonstrate that the occurrence of WHF during the hospital phase is associated with a significantly increased risk (2-3 times) of re-hospitalization and mid- and long-term morbidity and mortality outcomes (Cotter et al 2010; Weatherley et al 2009; Zannad et al 2013; Metra 2010; Teerlink et al 2013; Metra 2011; McMurray et al 2007).

Serelaxin is a recombinant form of human relaxin-2, a naturally occurring peptide hormone which is present in both men and women (Dschietzig et al 2006). The hormone rises to pharmacologic levels during pregnancy, being associated with many of the maternal hemodynamic and reno-vascular adjustments in response to the demands of pregnancy, such as increased cardiac output, increased renal blood flow, and increased arterial compliance (Teichman et al 2010, Du et al 2010, Conrad and Shroff, 2011). More recently, cardiac pleiotropic effects at the tissue level, i.e. contractility increase, angiogenesis, anti-inflammatory, prevention of ischemic-reperfusion injuries and extracellular matrix remodeling have been described.

Serelaxin represents a new pharmacologic class (relaxin peptide family) that is thought to help in AHF by stimulating vasodilation and renal function, boosting cardiac output and decreasing systemic vascular resistance.

Its efficacy and safety in AHF patients has been demonstrated in two studies, the dose-finding phase II study Pre-RELAX-AHF (Teerlink et al 2009) and the phase III pivotal study RELAX-AHF (Teerlink et al 2013, Metra et al 2013). Both the Pre-RELAX-AHF and the RELAX-AHF were randomized, double-blind, placebo-controlled, parallel-group, international trials comparing the intravenous administration of serelaxin for up to 48 hours, started within 16 hours of presentation, added to conventional therapy with placebo in patients hospitalized for AHF with dyspnea, congestion on chest radiography, increased natriuretic peptide levels, mild to moderate renal insufficiency, and systolic blood pressure >125 mmHg.

In the Pre-RELAX-AHF study 234 patients were enrolled, 230 of whom treated with serelaxin at 10, 30, 100 and 250 µg/kg/day or placebo (n=61, 40, 42, 38, 49 patients, respectively). The results showed beneficial effects of serelaxin on both dyspnea and post-discharge clinical outcomes. Serelaxin rapidly improved shortness of breath at 6 hours which was sustained at 12 and 24 hours, with 40% of subjects reporting moderate to marked improvement in the 30 µg/kg/day group, compared with 23% in the placebo group (p=0.044). Similar trends were seen with multiple outcomes including greater weight loss, lower intravenous (IV) loop diuretic use and lower incidence of in-hospital worsening heart failure in the serelaxin groups

(with the 30 µg/kg/day dose group being optimal) compared with placebo. Serelaxin was well tolerated at all doses, the adverse events (AEs) being distributed across study groups without any consistent pattern, the majority of which represented the natural history of patients admitted with AHF.

In the RELAX-AHF study 1161 patients were enrolled, 1138 of whom treated with serelaxin at 30 µg/kg/day or placebo (n=568 and 570 patients, respectively). The results showed a significant relief of dyspnea as measured by change from baseline on a 100-point visual analogue scale (VAS) over 5 days ($p=0.0075$), even though dyspnea reduction as measured using a 7-point, Likert scale over the first 24 hours (primary end-points) did not achieve statistical significance. The results also showed that, compared with conventional therapy, treatment with serelaxin improved signs and symptoms of patient congestion at Day 2 and significantly reduced WHF episodes through Day 5 and the overall length of index hospital stay, associated with a range of other in-hospital clinical benefits. WHF rates were significantly decreased by serelaxin in RELAX-AHF: significantly fewer patients in the serelaxin group experienced WHF event or death through Day 5 compared with the placebo group (6.5% vs. 12.0%, OR=0.51; 95% CI: 0.33, 0.77; RLX.CHF.003; data on file). Similar results were obtained for WHF through 14 days in placebo group 15.7% (KM) and serelaxin 11.4% (KM), $p=0.024$ ([Teerlink et al 2013](#)). Serelaxin provided sustained benefits beyond the initial 48 hours of infusion leading to a clinically and statistically significant 37% reduction in the risk of both cardiovascular and all-cause-mortality through Day 180. Serelaxin had favorable effects on the short-term changes in multiple laboratory markers of cardiac, renal, and hepatic damage known to be associated with long-term mortality in AHF. Serelaxin was well tolerated with no notable difference in the overall AE profile; a lower rate of AEs related to renal impairment in the serelaxin treatment arm compared with placebo was noted.

Based on these data, serelaxin represents a new treatment option in AHF, in addition to standard therapy, that may provide rapid and sustained dyspnea relief and improvement of other symptoms and signs of congestion. The findings obtained suggest serelaxin holds promise as the first evidence-based therapy for AHF to substantially improve patients' symptoms and clinical outcomes, including death.

1.2 Purpose

This is a multinational, multicenter, prospective, randomized, open label study to confirm and expand the efficacy, safety and tolerability evidence of 48 hours intravenous infusion of serelaxin (30 µg/kg/day) when added to Standard of Care (SOC), in patients admitted to hospital for AHF.

2 Study objectives

2.1 Primary objective(s)

[figure not shown]
The primary objective of the study is to evaluate the effect of serelaxin as add-on therapy to standard of care (SOC) versus SOC alone in reducing in-hospital worsening HF (WHF) requiring rescue therapy or all-cause death, from randomization through Day 5.

2.2 Secondary objectives

The secondary objectives of the study are the following:

- To assess the effect of serelaxin as add-on therapy to SOC versus SOC alone in reducing in-hospital WHF requiring rescue therapy or all-cause death or readmission for heart failure, from randomization through Day 14.
- To assess the effect of serelaxin as add-on therapy to SOC versus SOC alone in reducing the number of patients with persistent symptoms or signs of HF / not showing an improvement versus baseline conditions from randomization through Day 5 (persisting need of IV therapy for HF).
- To evaluate the effect of serelaxin as add-on therapy to SOC versus SOC alone in reducing the rate of renal deterioration (defined as ≥ 0.3 mg/dL increase in serum creatinine), from randomization through Day 5.
- To evaluate the effect of serelaxin as add-on therapy to SOC versus SOC alone in modifying the index length of stay (LOS) by location (e.g., ICU, CCU, cardiology department) in days and hours (ICU).
- To evaluate the safety and tolerability of intravenous serelaxin in AHF patients during a period of 30 days following exposure.
- To collect data on health-related quality of life (HRQoL) and economic burden to provide a more comprehensive analysis of the burden of HF, beyond the clinical outcomes.

3 Investigational plan

[figure not shown]
3.1 Study design

This study is a prospective, multinational, multicenter, randomized, open label clinical trial to evaluate the efficacy, safety and tolerability of serelaxin as add-on therapy to SOC versus SOC alone in AHF subjects on the primary composite end-point of in-hospital WHF or all-cause-death through Day 5. The outcome defined as in-hospital WHF (with signs/symptoms of worsening conditions, requiring therapy intensification) will be adjudicated by an Independent Board.

After signing an Ethics Committee or Institutional Review Board approved Informed Consent Form, subjects will be asked to undergo screening procedures for study eligibility. It is essential that screening is completed in time to allow randomization within 16 hours from presentation. Investigators are invited to initiate the serelaxin treatment as soon as possible after randomization.

After assessing patient eligibility during the screening period, patients who meet the study inclusion and none of the exclusion criteria will be randomized in a 2:1 ratio to receive intravenous infusion of either serelaxin for up to 48 hours in addition to SOC or SOC alone (Figure 3-1).

Figure 3-1 Study design

Presentation starts as the earliest of (1) time of presentation at either the ER/ED, ICU/CCU or ward (excludes EMS or other pre-hospital care); or (2) time of first IV loop diuretic for treatment of the current AHF episode prior to arrival at the hospital (this includes outpatient clinic, ambulance, or previous hospital including emergency department). Investigators will be encouraged to initiate therapy as soon as possible.

Serelaxin drug infusion will be administered via continuous IV infusion for 48 hours according to a weight-range adjusted dosing regimen at the nominal dose of 30 µg/kg/day. Due to the potential risk of hypotension, blood pressure will be monitored regularly during the administration of study drug. If at any time during dosing, the subject's systolic blood pressure is decreased by >40 mmHg from pre-treatment (i.e. just before the study drug infusion) but is ≥100 mmHg in 2 consecutive measurements 15 minutes apart, serelaxin infusion rate will be decreased by 50% for the remainder of the 48-hour study drug administration. Serelaxin administration will be permanently discontinued at any time if in 2 consecutive measurements, 15 minutes apart, systolic blood pressure is reduced to <100 mmHg. Measures may be taken by the investigator to address the decrease in blood pressure during the intervening 15 minutes, if clinically indicated. Should the study drug dose be decreased or the study drug be discontinued prematurely due to blood pressure decrease, then blood pressure measurements shall be taken every half hour through 2 hours following the blood pressure decrease event, and then hourly through 5 hours after the event onset. Upon completion of the 5-hour post event onset time point, heart rate and blood pressure measurements shall be resumed as outlined in [Section 6.5.2](#). If hypotension persists beyond the 5-hour post event onset, continued hourly blood pressure monitoring should be considered by the investigator, if clinically indicated. Additional blood pressure data collected beyond the 5-hour post event shall be reported in the source documents; only heart rate and blood pressure outlined in [Section 6.5.2](#) will be entered into the case report form (eCRFs).

Patients will be monitored closely during the treatment infusion period (48 hours up to Day 2). The study includes a short-term follow-up through Day 5, discharge and through Day 14. An extension follow-up period up to Day 30, when all subjects will receive a phone call to ascertain vital status and the need for repeated hospitalization.

Patients will undergo clinical evaluations including AHF symptom assessments, vital signs, physical examination emphasizing signs of HF, as well as the need for further IV or oral HF treatment and the occurrence of worsening HF events at least daily while hospitalized and then at Day 14. Subjects randomized to either serelaxin arm or SOC, and discharged prior to Day 5 will be required to return to the hospital/clinic for scheduled visits at Days 5 and 14. Should the patient not be able to come for the scheduled visit at Day 14, every effort should be made to contact the patient via phone to obtain essential vital details (See [Table 6-1](#)).

Safety will be assessed by monitoring AEs and vital signs and performing physical examinations and routine clinical laboratory tests as per protocol, as well as tests felt to be clinically indicated by the investigator up to Day 30.

To ensure patient safety, every SAE, regardless of causality, occurring after the patient has provided informed consent and through Day 14 must be reported to Novartis within 24 hours of learning of its occurrence. Any SAEs experienced after Day 14 should be reported to Novartis only if the investigator suspects a causal relationship to study treatment.

Patients are required to receive standard of care treatment for HF during both the index hospitalization and post-discharge per local and institution practice guidelines.

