remainder of the 48-hour study drug administration. Serelaxin administration will be permanently discontinued at any time if in 2 consecutive measurements; 15 minutes apart, systolic blood pressure is reduced to <100 mmHg.

Table 5-2 describes the actions required for a systolic BP decrease during the period of study drug infusion, which must be strictly followed.

Table 5-2 Dosing adjustment of study drug administration in the event of systolic BP decrease through completion of study drug infusion

Changes in systolic BP during infusion*	Adjustments of study drug administration
Decrease >40 mmHg from pre-treatment (i.e., measured just before the immediate start of study drug infusion), but systolic BP remains ≥ 100 mmHg	Reduce the infusion rate by half for the remainder of the study drug administration, i.e., reduce infusion rate from 10 mL/hour to 5 mL/hour for the remainder of 48-hour infusion
Decrease in absolute value of systolic BP to <100 mmHg	Permanently terminate study drug infusion

* These systolic BP values should be confirmed by two measurements taken 15 minutes apart.

In addition, dosing may be discontinued at any time at the discretion of the investigator. Reasons the investigator may discontinue study drug administration include, but are not limited to, serious or intolerable AEs suspected to be related to study drug. If dosing is discontinued for BP decreases, or any safety reasons, it should not be restarted. Re-administration of study drug once terminated for safety reasons is not allowed. The total time from initiation of study drug infusion to completion must not exceed 48 hours. In the event that study drug administration is discontinued, regardless of the reason, the patient will continue to be followed at all study visits defined in the protocol. These changes in study drug dose must be recorded on the Dosage Administration Record eCRF.

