6.5.2 Vital signs

Body temperature and respiratory rate will be measured at Screening, at 6, 12, 24 and 48 hours after start of study drug infusion in serelaxin arm and daily through index hospitalization, at Day 5, at discharge, and then at Day 14. Patients discharged prior to Day 5 will return to the hospital/clinic for Day 5 procedures. For the SOC patients, body temperature and respiratory rate will be measured at Screening, at 6, 12, 24 and 48 hours after randomization and daily through index hospitalization, at Day 5, at discharge, and then at Day 14, according to the scheduled visits.

Daily measurements may be made and recorded by trained study personnel as well as trained healthcare personnel as part of their routine clinical duties.

BP and HR measurements should be performed for all patients at the beginning of the screening period (after ICF signature) and at the end of the screening period (prior to randomization).

For serelaxin patients, BP and heart rate (HR) measurements will be also performed before the immediate start of study drug administration (0 hours pre infusion start), throughout study drug infusion at 30 and 60 minutes, then every hour for the first 6 hours, and then every 3 hours, including night time hours. Post-infusion BP and HR are to be measured every 3 hours until 12 hours following end of infusion, then every 6 hours for 48 hours and then every 24

hours through index hospitalization, at Day 5, at discharge, and then at Day 14. For patients randomized to the SOC group, BP and HR measurements should be also performed at 6, 12, 24, 48 hours, including night time hours, daily through index hospitalization, at Day 5, at discharge, and then at Day 14.

All measurements should be performed as close as possible to specified timepoint.

BP and HR are to be measured with the patient in the same position and with the same equipment using the same arm throughout study drug infusion. These measurements may be made and recorded by trained healthcare personnel as part of their routine clinical duties, as well as trained study personnel.

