If at any time during dosing, the subject's systolic blood pressure decreases by >40 mmHg from the systolic blood pressure measured just before the start of study drug infusion but is \geq 100 mmHg in two consecutive measurements 15 min apart, serelaxin infusion rate will be decreased by 50% for the remainder of the 48 hour study drug administration. Serelaxin administration will be permanently discontinued at any time if in two consecutive measurements 15 minutes apart, systolic blood pressure is reduced to <100 mmHg (also see details in [Section 5.5.5](#)).

Should the study drug dose be decreased or the study drug be discontinued prematurely due to blood pressure decrease, measurements should be taken every half hour through 2 hours following the blood pressure decrease event, and then hourly through 5 hours after event onset. Upon completion of the 5-hour post event onset time point, heart rate and blood pressure measurements should be resumed as outlined above.

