	QT/QTcF >460 msec; females only	Female subjects with QT/QTcF ≤460 msec at BL
	QT/QTcF increase from BL >30 msec	Subjects with a non-missing value at BL and post BL
	QT/QTcF increase from BL >60 msec	Subjects with a non-missing value at BL and post BL
PR	PR >200 msec	Subjects with PR ≤200 msec at BL
	PR >220 msec	Subjects with PR ≤220 msec at BL
	PR > 200 msec and change from BL ≥25%	Subjects with PR ≤200 msec at BL
QRS	QRS >110 msec and change from BL ≥25%	Subjects with QRS ≤110 msec at BL
	QRS >120 msec and change from BL ≥25%	Subjects with QRS ≤120 msec at BL
Heart Rate	Heart rate >100 bpm and change from BL ≥25%	Subjects with heart rate ≤100 bpm at BL
	Heart rate <50 bpm and change from BL ≥25%	Subjects with heart rate ≥50 bpm at BL

In addition, shift tables comparing baseline ECG overall interpretation (normal, clinically insignificant abnormality, clinically significant abnormality) with Day 5/discharge ECG overall interpretation (normal, clinically insignificant abnormality, clinically significant abnormality) will be provided by treatment group.

A listing of clinically significant abnormalities in ECG evaluations will be provided.

Echocardiography

Echocardiography is not considered as study related procedures and is performed according to local diagnostic practice.

Overall interpretation will be described by providing the number and proportion of subjects in each category at each assessment time point by treatment group. Percentages will be computed considering patients with non-missing information at each assessment time point.

LV Ejection Fraction (%) will be described by means of summary statistics (i.e., number of observations, mean, standard deviation, median, first and third quartiles, minimum and maximum) at each assessment time point by treatment group.

Systolic blood pressure decrease event

	Statistical Analysis Plan
	Sponsor: NOVARTIS Protocol number: CRLX030A3301

A confirmed systolic blood pressure decrease event (CBPDE) is defined as systolic blood pressure decreases by > 40 mmHg from just before the study drug infusion at baseline but is ≥ 100 mmHg in 2 consecutive measurements 15 minutes apart, or if in 2 consecutive measurements 15 minutes apart, systolic blood pressure reduces to < 100 mmHg, as reported in the "Systolic blood pressure decrease event – vital signs" eCRF.

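### A pair of readings on either side of 100 mmHg meets neither the halving rule nor the stopping rule, although a smaller fall requires halving

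*Protocol*

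**What the plan says.** Protocol 3.1 sets two dosing rules for falls in systolic pressure (SBP) during the infusion.

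- **Halve the rate** if SBP "is decreased by >40 mmHg from pre-treatment (i.e. just before the study drug infusion) but is ≥100 mmHg in 2 consecutive measurements 15 minutes apart".
- **Stop for good:** "Serelaxin administration will be permanently discontinued at any time if in 2 consecutive measurements, 15 minutes apart, systolic blood pressure is reduced to <100 mmHg".

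Protocol 5.5.5 repeats both rules and introduces Table 5-2 as a table that "describes the actions required for a systolic BP decrease during the period of study drug infusion, which must be strictly followed". The table's halving row requires SBP to stay at 100 or above, and its footnote reads "These systolic BP values should be confirmed by two measurements taken 15 minutes apart". The same section adds that "dosing may be discontinued at any time at the discretion of the investigator".

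Protocol 6.5.2 sets the routine SBP checks during infusion: at 30 and 60 minutes, "then every hour for the first 6 hours, and then every 3 hours, including night time hours". A denser schedule (half-hourly to 2 hours, then hourly to 5 hours) applies only on a condition: "Should the study drug dose be decreased or the study drug be discontinued prematurely due to blood pressure decrease".

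SAP 5.3 builds its definition of a confirmed systolic blood pressure decrease event (CBPDE) from the same two conditions. The first is the halving condition. The second begins "or if in 2 consecutive measurements 15 minutes apart, systolic blood pressure reduces to" and gives the limit of less than 100 mmHg.

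**The concern.** Each rule needs both readings of a pair to fall in its own range. Nothing covers a pair in which both readings are more than 40 mmHg down but one is below 100 and the other is not. Such a patient has a confirmed fall of more than 40 mmHg and has also had a reading below 100, yet no action is required. A patient with a smaller confirmed fall must have the rate halved.

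The situation is foreseeable. Protocol 3.1 lets the investigator treat the low pressure between the two readings, so 95 followed by 102 is an ordinary sequence. Protocol 5.5.5 itself notes how much pressure fluctuates in these patients. Low-dose IV nitrates are allowed at entry only where SBP exceeded 150 mmHg at the start of screening, so the higher-pressure patients include some on a second vasodilator. Protocol 3.6 relies on mandatory adjustment and stopping rules as part of its risk argument.

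Two things are at stake. For the patient, the infusion continues at full rate on routine checks unless the investigator chooses otherwise. For the analysis, the patient counts as having no CBPDE by the written definition. SAP 5.3 uses that yes/no split for incidence, for the IV-nitrate comparison, and to compare baseline characteristics, concomitant medication, Day 5 worsening heart failure or death, and adverse events.

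**Working it through.** The plan gives no figure to reproduce; this is a check of the rules' logic.

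**Inputs.** The two rules (Protocol 3.1, 5.5.5, 6.5.2); infusion rates of 10 and 5 mL/h (Table 5-2); the check schedules (6.5.2); the upper SBP limit of 180 mmHg at the end of screening (4.2, exclusion 3); 2:1 randomization, 2,337 randomized at Amendment 4, planned total 3,183.

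**Step 1: where the gap begins.** Let P be pre-infusion SBP and take whole mmHg. A reading that counts for halving must lie between 100 and P − 41. That range is empty unless P is at least 141. At P = 140 or below, any fall of more than 40 is already below 100, so two such readings meet the stop rule and there is no gap. Above 140 the range holds m = P − 140 values: 1 at 141, 5 at 145, 10 at 150, 20 at 160 and 40 at 180.

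**Step 2: worked pairs at P = 150.**

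| Readings | Falls | Required action now |
|---|---|---|
| 108, 108 | 42, 42 | halve |
| 100, 100 | 50, 50 | halve |
| 95, 102 | 55, 48 | none |
| 102, 98 | 48, 52 | none |
| 109, 85 | 41, 65 | none |
| 99, 99 | 51, 51 | stop |

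The required action does not rise steadily with the depth of the fall. A run of 102, 98, 102, 98, 102 never triggers either rule.

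**Step 3: every pair enumerated.** Take readings down to 80, which gives 20 values below 100. Above P = 140 there are (20 + m)² pairs in which each reading is below 100 or more than 40 down. Of these, 20² = 400 stop, m² halve, and 2 × 20 × m = 40m get no action.

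| P | Pairs | Stop | Halve | No action |
|---|---|---|---|---|
| 141 | 441 | 400 | 1 | 40 |
| 145 | 625 | 400 | 25 | 200 |
| 150 | 900 | 400 | 100 | 400 |
| 160 | 1,600 | 400 | 400 | 800 |

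Every no-action pair straddles 100. These counts depend on the arbitrary floor of 80 and are not probabilities.

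**Step 4: consequence per event after hour 6** (48 − 6 = 42 of the 48 infusion hours). The rate stays at 10 instead of 5 mL/h, so over 3 hours 30 mL is given instead of 15 mL. The denser schedule requires readings at 0.5, 1, 1.5, 2, 3, 4 and 5 hours, which is 7. The routine 3-hourly schedule requires 1 or 2 in the same 5 hours, and the next may be up to 3 hours away.

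**Step 5: number still to be treated.** 3,183 − 2,337 = 846 patients remained, and 846 × 2/3 = 564 would be allocated to serelaxin. This is an upper bound on those a corrected rule could cover, not a count of patients with the problem.

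**The case against.** The best counter-argument is that the gap mostly closes itself. Both rules apply throughout the infusion, and the last reading of a straddling pair can be treated as a new first value that needs its own confirmation 15 minutes later. After that, either a rule applies or the pressure has recovered. A site could also read the Table 5-2 footnote as confirming only the fall of more than 40, and so halve the rate. Beyond that, Protocol 5.5.9 goes further than permitting a stop: the investigator must stop if continuing is judged harmful, and a stop for low pressure starts the denser checks. Hypotension adverse events are compared between arms separately (SAP 5.3).

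Part of this stands. The safeguards are real, a later qualifying pair still triggers a rule, and the CBPDE page of the eCRF is not available, so what sites actually entered cannot be known. Only the written definition can be faulted.

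But no text asks for a third reading, the halving row says pressure must stay at 100 or above, and an alternating series stays unresolved even on the generous reading. If sites resolve the ambiguity differently, a rule meant to be uniform is not. Recovery to 100 or above is a good reason not to stop permanently; it does not explain why halving is skipped as well.

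A further objection is that changing the definition late in recruitment makes events before and after the change less comparable. That is a fair cost, and it is counted under the fix.

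**Conclusion.** The concern holds on the literal text. For any pre-infusion SBP above 140 mmHg, a pair of readings both more than 40 mmHg down and straddling 100 requires no dose change and no intensified checks, and it does not meet the CBPDE definition. A milder fall brings all three.

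The effect per event is a full instead of a halved infusion rate and, after hour 6, 1 or 2 required checks in 5 hours instead of 7. How often it happens cannot be estimated from the documents, so no percentage is claimed. The conclusion assumes that both conditions of the halving rule apply to each reading, as Protocol 3.1 and Table 5-2 are worded, and that the investigator does not act on discretion. The primary endpoint, alpha and power are not affected. It should be corrected, because it is a flaw in a mandatory safety rule, but it does not threaten the trial's main conclusion.

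**What to change.** **Dosing rule.** In Protocol 3.1, 5.5.5 with Table 5-2, 6.5.2 and Table 6-1 footnote 0, and in SAP 2.4, Table 2.6-1 footnote 0 and 4.2, state: *Stop if both of two consecutive readings 15 minutes apart are below 100 mmHg. Otherwise halve the rate if both are more than 40 mmHg below pre-infusion SBP, even if one of them is below 100 mmHg.* The stop rule in Protocol 5.5.9 needs no change, and the denser checks then follow from the dose decrease. With this wording the no-action column in the enumeration is 0 at every pre-infusion SBP. A 95/102 pair from 150 mmHg is halved, and 95/98 still stops.

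**Event definition.** In SAP 5.3, define a CBPDE as two consecutive readings 15 minutes apart, each of which is below 100 mmHg or more than 40 mmHg below pre-infusion SBP. This matches the set of pairs that lead to action. Tell sites to enter such pairs on the existing event page. Past pairs without a dose change fit the existing action category of none.

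**Optional addition.** If the second reading is the one below 100, ask for a repeat at 15 minutes, since the denser schedule would otherwise next require one at 30.

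**Cost.** One repeated sentence and a site instruction, carried through the usual amendment approvals; no new eCRF page. Expect slightly more dose reductions, slightly lower serelaxin exposure and a slightly higher CBPDE rate. For patients already treated, straddling pairs can be recovered only where both readings were recorded, because the 15-minute repeat is not a scheduled measurement.
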